7.3.9. Status of pregnancy (female patients only)

The status of pregnancy from the date of commencement of XELJANZ treatment to the date of completion of the observation period (or date of XELJANZ discontinuation) should be recorded. However, for patients who are treated with XELJANZ for more than 60 weeks after the date of treatment commencement, the status of pregnancy until the end of the investigation period (or date of XELJANZ discontinuation) should also be recorded.

7.3.10.Status of treatment with XELJANZ

The status of treatment with XELJANZ at the completion of the observation period for each booklet (Week 26, Week 60, end of the investigation) should be confirmed, and the following information should be recorded. If the reason for discontinuation at the last observation is an adverse event or patient's death, its details should be recorded in the adverse event field.

- 1. Date of the last observation
- 2. Completion of treatment or reason for discontinuation
 - Completed (treatment continued)
 - Adverse events (Record the details in the adverse event field)
 - Patient's death (Record the date of death)
 - Remission
 - Insufficient clinical effectiveness
 - Failure to show up
 - Other

7.3.11.Adverse events

The status of occurrence of adverse events from the date of commencement of XELJANZ treatment to the date of completion of the observation period (or date of XELJANZ discontinuation) should be confirmed, and the following information should be recorded. However, for patients who are treated with XELJANZ for more than 60 weeks after the date of treatment commencement, the record of malignant tumor and adverse events leading to discontinuation that occur at and after Week 61 should include the following information.

Occurrence of a serious adverse reaction, an unexpected adverse reaction or other adverse reactions should be separately investigated in detail if determined necessary by Sponsor.

- Presence/absence of adverse event
- Name of adverse event
- Diagnosis of malignant tumor (only if malignant tumor occurs)
- Date of occurrence
- Intervention
- Seriousness
- Outcome at the completion of observation period
- Causal relationship

If the adverse event is associated with abnormal laboratory values, i.e., clinical laboratory tests, the following information should also be recorded.

- Laboratory parameter
- Site reference value
- Unit
- Date measured

• Results

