All adverse events (AEs) occurring from the start of treatment to the end of the observation period will be collected for patients whose observation period is 60 weeks or less. For patients whose observation period exceeds 60 weeks, all AEs will be collected until 60 weeks and thereafter only malignancies and AEs leading to discontinuation of treatment will be collected.

• Analysis for safety evaluation

In the safety analysis set, the onset of major adverse reactions (AEs considered by the physician to be related to this drug), incidence of adverse reactions (number/percentage of patients with adverse reactions), and incidence of adverse events per duration of exposure (100 × number of patients with adverse reactions / total duration of exposure / 100 person-years) will be set as primary analysis items. In addition, factors that may affect the onset of adverse reactions will also be examined by conducting subgroup analyses based on patient background and other factors.

• Analysis for effectiveness evaluation

In the effectiveness analysis set, the rate of remission based on partial Mayo score will be set as primary analysis items.

• Dosage and administration of this drug

For induction, the recommended dose of this drug is 10 mg administered twice daily (10 mg BID [bis in die]) for 8 weeks. If the response is inadequate after the 8 weeks course of treatment, another 8 weeks course may be administered.

For maintenance, the recommended dose is 5 mg twice daily (5 mg BID). If the response decreases during the maintenance, the dose level may be increased to 10 mg BID. Intractable patients for whom prior drug therapies (e.g., a TNF inhibitor) were ineffective may be treated with 10 mg BID.

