6. ENDPOINTS AND COVARIATES

6.1. Safety Endpoints

The safety endpoints and their definition in this study are presented below. Events assessed as a safety endpoint will be those that developed from the start of treatment to the end of observation period or 60

weeks after the start of treatment, whichever came first, except for malignancies, for which all events occurring by the end of observation period will be assessed as a safety endpoint.

- Adverse reactions: Adverse events considered by the physician as treatment-related
- Adverse events (AEs): All-causality AEs
- Serious adverse events (SAEs) and serious adverse reactions: AEs and adverse reactions considered by the physician as serious
- Safety specification: The definition of the events considered as an element in the safety specification of this drug should follow the definition of the Important Identified Risks and Important Potential Risks presented in the Appendix of the latest Tofacitinib Periodic Safety Update Report (PSUR). Below is the definition at the time of the preparation of this SAP (3.0 version), except for hepatitis B virus reactivation, of which definition is given in this SAP below, because it is not defined in the PSUR.
 - Serious infections (including tuberculosis, pneumonia, pneumocystis pneumonia, sepsis, opportunistic infection): Events that are serious and coded as MedDRA SOC Infections and Infestations; MedDRA HLT Tuberculous infections, Mycobacteria identification and serology; MedDRA PT Febrile neutropenia, Asymptomatic COVID-19, Coronavirus infection, Coronavirus test positive, Coronavirus test, COVID-19 immunisation, COVID-19 pneumonia, COVID-19 prophylaxis, COVID-19 treatment, COVID-19, Exposure to SARS-CoV-2, Occupational exposure to SARS-CoV-2, SARS-CoV-2 antibody test, SARS-CoV-2 antibody test positive, SARS-CoV-2 carrier, SARS-CoV-2 sepsis, SARS-CoV-2 test false negative, SARS-CoV-2 test positive, SARS-CoV-2 test, SARS-CoV-2 viraemia, or Suspected COVID-19
 - Herpes zoster: Events coded as MedDRA PT Disseminated varicella zoster virus infection,
 Genital herpes zoster, Herpes zoster cutaneous disseminated, Herpes zoster
 disseminated, Herpes zoster infection neurological, Herpes zoster meningitis, Herpes zoster
 meningoencephalitis, Herpes zoster meningomyelitis, Herpes zoster necrotising retinopathy,
 Herpes zoster oticus, Herpes zoster pharyngitis, or Ophthalmic herpes zoster

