 - Neutrophils decreased, lymphocytes decreased, and haemoglobin decreased: Events retrieved by MedDRA SMQ Haematopoietic erythropenia (Broad and Narrow); or coded as MedDRA PT Agranulocytosis, Band neutrophil count decreased, Band neutrophil percentage decreased, Cyclic neutropenia, Febrile neutropenia, Granulocyte count decreased, Granulocytopenia, Idiopathic neutropenia, Neutropenia, Neutropenic infection, Neutropenic sepsis, Neutrophil count decreased, Neutrophil percentage decreased, B-lymphocyte count decreased, Lymphocyte count decreased, Lymphopenia, T-lymphocyte count decreased, or Lymphocyte percentage decreased
 - Hepatic function disorder: Events retrieved by MedDRA SMQ Drug related hepatic disorders severe events only (Narrow); or coded as MedDRA PT Alanine aminotransferase increased,
 Aspartate aminotransferase increased, Hepatic enzyme increased, or Transaminases increased
 - Hepatitis B virus reactivation: Events associated with hepatitis B that developed in patients with
 past history of hepatitis B virus carrier or with a complication of hepatitis B virus carrier

- Gastrointestinal perforation: Events retrieved by MedDRA SMQ Gastrointestinal perforation
 (Narrow); or coded as MedDRA PT Abscess bacterial, Abscess rupture, Appendicectomy,
 Appendicitis, Biliary abscess, Colitis, Diverticulitis, Diverticulum, Gallbladder abscess, Liver
 abscess, Pancreatic abscess, Pelvic abscess, Perihepatic abscess, Postoperative abscess, Pyloric
 abscess, Rectovaginal septum abscess, Splenic abscess, or Subdiaphragmatic abscess
- Interstitial lung disease: Events retrieved by MedDRA SMQ Interstitial lung disease (Broad and Narrow)
- Venous thromboembolism: Events retrieved by MedDRA SMQ Embolic and thrombotic events, venous (Narrow)
- Malignancy: Events retrieved by MedDRA SMQ Malignancy related conditions (Narrow),
 Malignancy related therapeutic and diagnostic procedures (Narrow), Malignant or unspecified tumours (Narrow), or Tumour markers (Narrow)

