8.1.4. Analyses based on the person-year method

The incidence of an event per exposure duration will, if it should be presented, be calculated using the following formula:

Incidence (patients/100 patient-year) = $100 \times y/PT$

y: Number of patients who experienced the event

PT: Total exposure duration (years),

Here the exposure duration for event-free patients will be given by the period from the start of treatment to the end of the observation period unless this exceeds 60 weeks; if this period exceeds 60 weeks, the exposure duration should be 60 weeks. The exposure duration for patients who experienced the event is, in principle, the period from the start of treatment to the day the event was first observed, but if the event occurred 60 weeks or later after the start of treatment, the patient will be handled as an event-free patient and their exposure duration should be 60 weeks. For malignancy, however, no such upper limit will be set; the exposure duration for malignancy-free patients will be the period from the start of treatment to the end of the observation period, while the exposure duration for patients in whom malignancy developed will be the period from the start of treatment to the day of the first observation of the event. The 95% CI will be calculated using the following formula:

$$\left[\frac{100}{PT} \times \frac{1}{2} \chi_{2y}^{2}(\alpha/2), \frac{100}{PT} \times \frac{1}{2} \chi_{2(y+1)}^{2}(1-\alpha/2)\right]$$

y: Number of observed events

 $\chi^2_{2\nu}(\alpha/2)$: The $\alpha/2$ -fractile point of the chi-square distribution with 2y degrees of freedom

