8.2.3. Safety analyses

Adverse reactions or AEs included in a summarization will be those that developed from the start of treatment to the end of the observation period or 60 weeks after the start of treatment, whichever came first, except for malignancy, for which all events occurring by the end of observation period will be included in a summarization. All adverse reactions and AEs reported in this study will be included in a listing.

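### The malignancy element is wider than what must be reported after Week 60, yet it is analysed without a cap across both periods, which may bias the late and pooled rates downward

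*SAP*

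**What the plan says.** **Definition.** SAP 6.1 builds the malignancy element from four narrow SMQs. Beyond malignancy-related conditions it takes in "Malignancy related therapeutic and diagnostic procedures (Narrow), Malignant or unspecified tumours (Narrow), or Tumour markers (Narrow"). The list is tied to the definition "presented in the Appendix of the latest Tofacitinib Periodic Safety Update Report (PSUR"), so it can change with that report.

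**Collection.** For patients observed beyond 60 weeks, SAP 2.1 states that "all AEs will be collected until 60 weeks and thereafter only malignancies and AEs leading to discontinuation of treatment will be collected". Protocol 7.3.11 uses a narrower term for what sites must enter on the CRF: "the record of malignant tumor and adverse events leading to discontinuation that occur at and after Week 61". Footnote 10 to the protocol's schedule of observation names the same two classes. In both periods the CRF has an item "Diagnosis of malignant tumor (only if malignant tumor occurs").

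**Analysis.** SAP 8.1.4 stops person-time at 60 weeks for every other element, then adds: "For malignancy, however, no such upper limit will be set". SAP 8.1.5 does the same for the Kaplan-Meier plot. SAP 8.2.3 limits summaries to 60 weeks "except for malignancy, for which all events occurring by the end of observation period will be included in a summarization". The onset bands for malignancy in 8.2.3.1 to 8.2.3.3 continue past Week 60; in 8.2.3.1 and 8.2.3.3, six of the ten lie beyond it. No analysis restricted to diagnosed malignant tumours is specified.

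**The concern.** The numerator follows one reporting rule before Week 60 and a narrower one afterwards, while the denominator carries on unchanged. A pooled rate built this way is neither the rate of the SMQ element nor the rate of diagnosed malignancy, and a comparison of early with late bands partly compares collection rules.

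This matters because malignancy is listed in SAP 2.1 as an important identified risk, is the only element analysed beyond Week 60, and is meant to be examined for change in risk over time (8.2.3.3). The plan also already accepts the principle at issue. Other elements are collected after Week 60 only when they lead to discontinuation, and the SAP caps all of them at 60 weeks. The non-diagnostic part of the malignancy element is collected in the same partial way but is not capped.

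**Working it through.** The plan states no malignancy rate, so there is no figure to reproduce. The check sets the collection rules side by side and then sizes the effect under stated assumptions.

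**Step 1: what is captured when** (protocol 7.3.11 and footnote 10 to Table 2; SAP 2.1 and 6.1)

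| Report falling in the SMQ element | To Week 60 | From Week 61 |
|---|---|---|
| Diagnosed malignant tumour | collected | collected |
| Marker, procedure or unspecified tumour, no diagnosis, led to discontinuation | collected | collected |
| The same, did not lead to discontinuation | collected | not required by the protocol's wording |

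Only the third row changes at Week 60.

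**Step 2: the ratio under a constant risk.** SAP 8.1.4 counts patients, timed at the first event, so the shares are defined on patients' first element events:

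- s = share that are not a diagnosed malignant tumour (not in the documents; assumed 0 to 0.5)
- d = share of those that lead to discontinuation (not in the documents; assumed 0 to 1)

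With a constant element rate λ, the rate observed before Week 60 is λ. Afterwards it is λ(1 − s) + λsd = λ[1 − s(1 − d)]. The late/early ratio is therefore 1 − s(1 − d).

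| s | d = 0 | d = 0.5 | d = 1 |
|---|---|---|---|
| 0 | 1.00 | 1.00 | 1.00 |
| 0.1 | 0.90 | 0.95 | 1.00 |
| 0.3 | 0.70 | 0.85 | 1.00 |
| 0.5 | 0.50 | 0.75 | 1.00 |

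These figures treat every unreported late event as lost. A patient diagnosed later while still under observation would be counted, with a later onset date, so for such patients the effect is on timing and not on the count.

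**Step 3: the pooled rate.** Illustration, all inputs assumed: λ = 1 per 100 patient-years, 300 patient-years before Week 60 and 200 after.

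- s = 0.3, d = 0: expected late events are 2.0 × 0.70 = 1.4, and the pooled rate is 100 × (3.0 + 1.4)/500 = 0.88 per 100 patient-years. This lies between the full-element rate of 1.00 and the diagnosed-tumour rate of 0.70.
- s = 0.1, d = 0.5: expected late events are 2.0 × 0.95 = 1.9, and the pooled rate is 100 × (3.0 + 1.9)/500 = 0.98.

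**Step 4: could the data reveal it?** By the exact interval in SAP 8.1.4, 2 events in 200 patient-years give 1.00 per 100 patient-years with a 95% CI of 0.12 to 3.61. A shortfall of 0.1 to 0.6 expected events could be neither seen nor excluded.

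**Step 5: after the fix.** If only events collected under the same rule in both periods are counted, the ratio is 1.00 under a constant risk for any s and d.

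**The case against.** A reader might infer two stronger things: that nothing but malignant tumours is collected after Week 60, and that the plan will therefore show a false late fall of 1 − s. The documents support neither. Events leading to discontinuation are still collected, which is why d belongs in the formula. The documents give no value for s, and it may be small: the laboratory list in protocol 7.3.7.1 has no tumour-marker heading, a marker change enters only as a clinically significant adverse event, and a marker or procedure report in a patient who also has a diagnosed tumour adds nobody to the numerator. A rising true risk could also hide any shortfall.

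The plan has further defences:

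- **Wording.** SAP 2.1 says *malignancies*, which could be read as the whole element. The protocol tells sites to record *malignant tumor*, and neither document defines the term for reporting, so the wider reading is possible but not secured.
- **Transparency.** The onset bands break exactly at 60 weeks, safety-specification events are tabulated by preferred term, and all are listed. A careful reader could pick out marker-only cases. This stands for the bands taken one at a time; it does not repair the pooled incidence or the Kaplan-Meier curve, and a comparison across Week 60 still needs a warning.
- **PSUR consistency.** Keeping the PSUR definition serves consistent safety reporting, and a diagnosis-only count would drop unspecified tumours that led to discontinuation, although these are collected throughout. This is a reason to keep the PSUR row as well, not to run it uncapped.

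The analyses are descriptive, and imprecision will dominate with few events. That limits how much weight the point carries.

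**Conclusion.** The mismatch between definition and collection holds on the documents' wording. Non-diagnostic reports that do not lead to discontinuation are collected before Week 60 but not necessarily after it, while the incidence, Kaplan-Meier plot and onset bands span both periods. Any resulting bias lowers the late rate, and the pooled rate with it, relative to the full element. Its size cannot be obtained from the documents: the late/early ratio runs from 1.00 (s = 0 or d = 1) to 0.50 (s = 0.5, d = 0) over the assumed range. The conclusion rests on reading the protocol's term as a diagnosed malignant tumour and, for the ratio, on a constant underlying risk. A false late decline is possible, not demonstrated. The point is worth acting on because the remedy is cheap and uses data already collected.

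**What to change.** 1. In every uncapped malignancy analysis (SAP 8.1.4, 8.1.5 and the onset bands in 8.2.3.1 to 8.2.3.3), count patients with a malignant-tumour diagnosis recorded on the CRF under protocol 7.3.11, since that item is collected in both periods.
2. Show the full PSUR/SMQ element as a separate row, capped at 60 weeks like the other elements.
3. Add a note to these outputs that collection changes at Week 60, and state in the SAP what counts as a reportable malignancy from Week 61.

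The cost is some SAP wording and one extra row per table. The uncapped count may be slightly smaller than the count under the PSUR definition. Unspecified tumours after Week 60 that led to discontinuation would appear only in the listings.

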6.2. Efficacy Endpoints

Effectiveness will be evaluated using the Mayo score tool. The Mayo score depends on four subscores, each of which ranges from 0-3 with higher scores indicating severer disease activity. The four subscores indicate the disease activity assessed in terms of stool frequency (score range: 0-3), rectal bleeding (0-3), mucosal appearance at endoscopy (0-3), and physician's global assessment (0-3).

The Mayo score is the sum of the four subscores and ranges from 0-12. The partial Mayo score is defined as the sum of the three of the four subscores excluding the findings of flexible sigmoidoscopy subscore and ranges from 0-9.

In addition to Mayo scores, faecal calprotectin, which highly correlates with the degree of the inflammation of UC and can be determined noninvasively and more conveniently than colonoscopic measures, will also be used to assess the effectiveness of this drug.

In this study, the partial Mayo score will be used as the primary efficacy endpoint.

- Partial Mayo score: Stool frequency subscore + rectal bleeding subscore + physician's global assessment subscore
- Mayo score: Stool frequency subscore + rectal bleeding subscore + findings of flexible sigmoidoscopy subscore + physician's global assessment subscore
- Mayo subscores

Stool frequency:

0 point: Normal number of stools for the patient

1 point: 1-2 stools more than normal

2 points: 3-4 stools more than normal

3 points: 5 or more stools more than normal

Rectal bleeding:

0 point: None blood seen

1 point: Slight of blood with stool less than half the time

2 points: Obvious blood with stool most of the time

3 points: Blood alone passed

Findings of flexible sigmoidoscopy:

0 point: Normal or inactive disease

1 point: Mild disease (erythema, decreased vascular pattern, mild friability)

2 points: Moderate disease (marked erythema, absent vascular pattern, any friability, erosion)

3 points: Severe disease (spontaneous bleeding, ulceration)

Physician's global assessment:

0 point: Normal

1 point: Mild disease

2 points: Moderate disease

3 points: Severe disease

• Faecal calprotectin

6.3. Other Endpoints

Not applicable.

6.4. Covariates

Candidate covariates for the development of Serious infections (including Tuberculosis, Pneumonia, Pneumocystis pneumonia, Sepsis, and Opportunistic infection), Herpes zoster, and Malignancy considered in this study are shown below.

| Covariate | Serious infections | Herpes zoster | Malignancy |
|--------------------------------------|-----------------------|------------------|------------|
| Gender [reference: male] | 0 | 0 | 0 |
| Age [reference: <50 years] | 0 | 0 | 0 |
| Body weight [reference: <50 kg] | 0 | 0 | 0 |
| BMI [reference: <18.5 kg] | 0 | 0 | 0 |
| Duration of UC [reference: <2 years] | 0 | 0 | 0 |

NIS Protocol A3921248 Statistical Analysis Plan

Serious Herpes Covariate infections Malignancy zoster Severity of UC [reference: moderate] 0 Past history (Infections) [reference: absent] 0 0 Past history (Malignancy) [reference: absent] × X Past history (Lung disorder) [reference: absent] 0 × × Complications (Infections) [reference: absent] 0 0 X Complications (Malignancy) [reference: absent] 0 Complications (Hepatic function disorder) [reference: absent] 0 0 0 Complications (Hepatitis B) [reference: absent] X X 0 Complications (Hepatitis C) [reference: absent] X X 0 Complications (Renal impairment) [reference: absent] 0 \circ 0 Complications (Diabetes mellitus) [reference: absent] Ο 0 0 Smoking [reference: absent] 0 0 0 Family history of malignancy (including lymphoma) [reference: absent] Prior treatment with a 5-aminosalicylic acid preparation [reference: 0 0 0 absent] Prior treatment with steroid [reference: absent] 0 0 0 Prior treatment with an immunomodulator (azathioprine, 0 0 6-mercaptopurine) [reference: absent] Prior treatment with tacrolimus [reference: absent] Prior treatment with a biologic agent [reference: absent] 0 0 Baseline neutrophil count [reference: <2000/µL] 0 0 0 Baseline lymphocyte count [reference: <1000/μL] 0 0 \circ Prior vaccination with a herpes zoster vaccine [reference: absent] 0 0 × Prior vaccination with a pneumococcal vaccine [reference: absent] 0 Prior vaccination with a tuberculosis vaccine [reference: absent] 0 Prior vaccination with a pneumocystis jirovecii pneumonia vaccine [reference: absent] Prior vaccination with a hepatitis B vaccine [reference: absent]

o: Applied, ×: Not applied

Additional covariates may be included or some deleted after consideration based on an interim analysis of this study or emerging knowledge. If this will occur, this SAP will be revised.

7. HANDLING OF MISSING DATA

If the date of the end of the treatment with this drug is missing, the date of the last observation recorded in the CRF entry "Status of the treatment with Xeljanz" will be used instead. Treatment completers whose end-of-treatment date has not been recorded will be handled in a way that the treatment continued until the last observation date.

Similarly, if the date of the end of a drug therapy or non-drug therapy is missing, the date of the last observation will be used instead.

If the severity, action taken, or outcome for an AE is missing, it will be treated as "unknown" when summarizing data.

If an efficacy endpoint was not measured within its visit window (Appendix 1), it will be treated as missing data and no imputation will be done. The partial Mayo score will be treated as missing data unless the stool frequency subscore, rectal bleeding subscore, and physician's global assessment subscore have all been measured. Similarly, the Mayo score will be treated as missing data unless the stool frequency subscore, rectal bleeding subscore, findings of flexible sigmoidoscopy subscore, and physician's global assessment subscore have all been measured.

Cleaning-uncompleted data will be in principle handled as follows:

- Items for which data are missing: For both purposes of summarization and listing, the corresponding data will be treated as missing data (or as "unknown" if they are a categorical variable).
- Items for which data are inconsistent: For both purposes of summarization and listing, the inconsistent data will be treated as missing data. A list of how each set of inconsistent data have been handled will be presented separately.
- No signature: For both purposes of summarization and listing, any record in a CRF with no signature of a contract physician (including when the CRF is signed only by individuals other than contract physicians) will be treated as missing data.

With regard to analyses that involve the time to onset of each element in the safety specification, if development of an event has been reported in a patient but its onset date is unknown, the onset date will be imputed with the last date on which the patient can be confirmed to be free from the event in view of all kinds of data collected; the shortest possible date imputed may be the start date of treatment. For patients in whom development has not been reported but the date of the end of observation is unknown, the end date will be imputed with the last date on which administration of this drug can be confirmed in view of all kinds of data collected; the shortest possible date imputed may be the start date of treatment.

Missing data (including the case of "unknown") for candidate covariates (Section 6.4) will not be imputed in univariate analyses. For multivariate analyses, missing data for candidate covariates will be treated as a subcategory of the category "unknown".

